5. INTRODUCTION

5.1. Background

Hereditary angioedema (HAE) with C1-esterase inhibitor (C1-INH) deficiency is an autosomal dominant disorder characterized by recurrent episodes of swelling of the skin, pharynx, larynx, gastrointestinal (GI) tract, genitals, and extremities (Longhurst and Cicardi 2012). The frequency of attacks varies between subjects, from rarely in some patients to every few days in others. Angioedema attacks may or may not be precipitated by a stimulus (such as stress, trauma, or estrogen) and are typically rapid in onset, with symptoms subsiding gradually over the following 3 to 5 days (Zuraw and Christiansen 2011). Oropharyngeal swelling can be life-threatening (Bork, Hardt et al. 2012), while attacks in other sites, including limbs, genitalia, face and intestines, can be painful, disabling, and disfiguring, and have a significant impact on functionality and quality of life (QoL) (Lumry, Castaldo et al. 2010). Although mortality risk from asphyxiation is much higher in undiagnosed patients with HAE, deaths still occur in diagnosed patients with access to care at centers of excellence (Bork, Hardt et al. 2012).

Extensive evidence from animal models and clinical studies supports the role of bradykinin (BK) as the principal mediator of the signs and symptoms that characterize attacks of HAE (Kaplan 2010, Zuraw and Christiansen 2011). Plasma kallikrein is a serine protease integral to the contact activation pathway (Saxena, Thompson et al. 2011). Kallikrein circulates in plasma as a zymogen, prekallikrein (PKK), bound to one of its main substrates, high-molecular-weight kininogen (HK). During contact activation, PKK is cleaved by activated factor XII, forming the active protease kallikrein. Kallikrein in turn cleaves HK, producing BK (Kaplan and Ghebrehiwet 2010). The activation of the BK B2 receptor by BK ultimately results in vasodilatation, increased vascular permeability, and smooth muscle contraction, all of which lead to the tissue swelling that characterizes HAE (Kaplan 2010).

BCX7353 is a potent, synthetic, second-generation small molecule inhibitor of plasma kallikrein. In contrast to parenterally administered options commercially available for prophylaxis against HAE attacks, inhibition of kallikrein with an orally bioavailable small molecule such as BCX7353 offers the advantage of oral administration.

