Overall, 49.8% of subjects had at least 1 TEAE assessed as drug-related by the Investigator (ie, TEAEs possibly, probably, or definitely related to study drug). Most TEAEs were Grade 1 (mild) or Grade 2 (moderate) in severity. Overall, 15.0% of subjects experienced a Grade 3 or Grade 4 TEAE. The most common Grade 3 or Grade 4 TEAEs were HAE (attacks) (3.5%), ALT increased (2.6%), hepatic enzyme increased (0.9%), LFT abnormal (0.9%), and pneumonia (0.9%). All other Grade 3 or Grade 4 TEAEs occurred in 1 subject each. Overall, long term prior androgen use of ≥ 5 years and discontinuation of androgens within 2 weeks of BCX7353 initiation was correlated with a higher frequency of Grade 3 or Grade 4 liver-related TEAEs.

Overall, 13.2% of subjects experienced a treatment-emergent SAE. Treatment-emergent SAEs that occurred in > 1 subject were HAE attacks (12 subjects [5.3%]) and medical observation (3 subjects [1.3%]). Three subjects (1.3%) experienced 4 treatment emergent SAEs assessed by the Investigator as related to study drug; G3 gastroenteritis and Grade 2 hepatic enzyme increased (n = 1), G3 abnormal LFT (n = 1), and G3 abdominal pain (n = 1). The 2 subjects with the treatment-emergent SAEs of gastroenteritis, hepatic enzyme increased, and abnormal LFT discontinued study drug. No subjects experienced a TEAE that led to death.

Overall, 27 subjects (11.9%) interrupted study drug due to TEAEs. The most common TEAE that led to study drug interruption was HAE (attack) in 5 subjects (2.2%). Overall, TEAEs in the GI SOC led to study drug interruption in the greatest number of subjects; 8 subjects (6.3%) treated with BCX7353 150 mg and 2 subjects (2.0%) treated with BCX7353 110 mg. Overall, 6 subjects (2.6%) discontinued study drug due to a GI TEAE; 2 subjects (2.0%) and 4 subjects (3.1%) in the BCX7353 110 and 150 mg dose groups, respectively.

For this study, nonserious treatment-emergent rashes were considered EOSIs for Investigator reporting purposes. Overall, 8 subjects (3.5%) had rash EOSIs assessed by the Investigator as related to study drug but these rashes included non-specific urticaria and brief episodes of erythema. A total of 2 rash events were assessed by the Sponsor medical officer as likely related

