11.2.2. HAE Attack and Dosing Diary

The Sponsor will supply diaries to all sites. Sites will dispense diaries to subjects at screening. Diaries will be collected at each visit and at follow-up.

At the Screening visit, subjects will be instructed how to complete the diary for an attack. While a subject has a diary in their possession, the subject will fill out the HAE attack diary recalling whether symptoms of an HAE attack were experienced. Subjects need only to fill out the diary details section when there is presence of HAE symptoms. If the subject does report an attack in their diary, additional details about the attack will be required, including location of the symptoms of the attack, severity, and treatment(s) administered and times of administration.

Further training on completing the diary should be provided at each clinic visit.

While study staff are not permitted to make any entries into the diary, subjects may be asked to rectify incomplete diary entries made since the last visit based on outstanding questions a subject may have or incorrect assumptions/interpretation of diary questions.

Subjects should bring their diary to each study visit. It is also acceptable for completed diaries to be returned to the site on a monthly basis after Week 4.

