For the purposes of this protocol, HAE attacks and their associated symptoms will not be defined as AEs, even if the subject requires hospitalization. All HAE attacks and associated symptoms are reported in the subject diary and are a reflection of the disease under study. The events that may trigger a HAE attack such as an infection or trauma are considered AEs and should be reported as such.

Hospitalization scenarios do not require reporting as an SAE where there is no occurrence of an AE. These scenarios include a planned hospitalization or prolonged hospitalization to:

- Perform a routine control screening for a preexisting illness or to diagnose a suspected illness. In the case of the latter, the symptomatology should be reported as an AE and amended if a diagnosis is confirmed.
- Undergo a diagnostic or elective surgical procedure for a preexisting medical condition that has not changed (eg, a joint replacement for which the subject was on a waiting list).
- Undergo medical observation due to HAE (eg, admission after a routine dental procedure in an HAE patient).
- Undergo medical observation without the occurrence of an AE due to standard of care in the region or hospital.

Surgical procedures should not be reported as AEs. The condition for which the surgery is required should be reported as the AE, if it occurs or is detected during the study period. Planned surgical measures permitted by the clinical study protocol and the condition(s) leading to these measures are not AEs, if the condition(s) was (were) known before the start of study treatment. In the latter case the condition should be reported as medical history.

AEs are designated as “non-serious” or “serious.”

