12.1.1.2. Serious Adverse Event

A SAE is an AE/reaction that results in any of the following outcomes:

- Death
- Is life-threatening (subject is at immediate risk of death at the time of the event; it does not refer to an event that hypothetically might have caused death if it were more severe)
- Requires subject hospitalization (formal admission to a hospital for medical reasons) or prolongation of existing hospitalization
- Results in persistent or significant disability/incapacity (i.e., there is a substantial disruption of a person's ability to carry out normal life functions)
- Is a congenital anomaly/birth defect

Important medical events that may not result in death, are not life-threatening, or do not require hospitalization may be considered a SAE when, based upon appropriate medical judgment, they may jeopardize the subject's health or may require medical or surgical intervention to prevent one of the outcomes listed in this definition. For this study, examples of such events may include allergic bronchospasm requiring intensive treatment in an emergency room or at home, blood dyscrasias, or convulsions that do not result in subject hospitalization.

In addition, the Sponsor considers events of abortion (spontaneous or induced), fetal demise, and still birth as SAEs for reporting purposes.

Some hospitalization scenarios, as outlined in Section 12.1.1.1 do not require reporting as SAEs.

Overdose will be considered an SAE only if any of the seriousness criteria are met. Any clinical complication in association with the overdose should be reported as an AE or SAE (as applicable) along with the overdose (see Section 12.2.2). Details of signs or symptoms, clinical management and outcome should be reported, if available. Overdose without associated signs or symptoms should not be recorded as AEs but should be recorded as protocol deviations.

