## **5. PLANNED ANALYSES**

### **5.1. Interim Analyses**

DMC meetings will occur after the first 10 subjects have completed 12 weeks of treatment and every 12 weeks thereafter until the last enrolled subject completes 48 weeks, or as DMC meetings are conducted in concert for related BCX7353 studies.

Before each scheduled DMC meeting, a packet of summary materials will be prepared and distributed for the Committee's review. The packet will include study disposition, demographic, and safety information by treatment group. Study disposition will consist of the number of subjects screened, the number of subjects allocated to treatment, the number of subjects who received treatment, the number of subjects who completed the study, the number of subjects who were withdrawn from the study and the primary reasons for withdrawal, the number of subjects ongoing in the study, the number of subjects who completed dosing in the entire study, the number of subjects withdrawn from the study medication, and the primary reasons for withdrawal, and the number of subjects ongoing on study medication. Demographic information will consist of age, gender, race, ethnicity, weight, height, and body mass index (BMI).

Safety summaries will include an overall summary of TEAEs (overall numbers of subjects with TESAEs, TEAEs, drug-related TEAEs, TEAEs leading to discontinuation of study drug, Grade 3 or 4 TEAEs, and drug-related TEAEs of Grade 3 or 4), summaries of TEAEs by system organ class (SOC) and preferred term (PT), which include TESAEs, TEAEs, Grade 3 or 4 TEAEs, TEAEs leading to discontinuation of study drug, and summaries of subjects with treatment-emergent laboratory abnormalities overall and for each laboratory panel by parameter and grade. Relevant review materials will normally be sent to DMC members and open session participants 5 business days before each scheduled meeting.

All summary materials will be distributed via email.

An internal analysis will be conducted at the time of the BCX7353-302, Part 1 analysis. This analysis will be used to write the draft report for the BCX7353-204 study.

An interim analysis will be performed when approximately 100 subjects at either the 110 or 150 mg dose from a combination of studies BCX7353-204 and BCX7353-302 complete 48 weeks. Additionally, an integrated analysis of safety and effectiveness involving data from both studies will be performed. This analysis will be used for regulatory submissions.

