**Table 6: Determination of Attack Location Using Symptoms Collected in the Diary**

Abdominal-Only Attack	Mixed Attack	Peripheral Attack (Inclusive of Skin and Airway Swelling)
Symptoms checked must only come from this box: Internal swelling or symptoms of internal swelling in the abdomen: Nausea Abdominal discomfort Cramps (colicky pain) Vomiting Abdominal pain Diarrhea	Must have at least 1 symptom from left and right box (from abdominal and peripheral attack characterization)	Symptoms checked must only come from this box: Visible swelling: face/head neck (outer swelling) legs, buttocks/genitals eyes arms feet stomach (outside) mouth/tongue/lips hands chest/back joints Internal swelling or symptoms of internal swelling of the airways: lump in throat/tightness change in voice difficulty swallowing difficulty breathing Pink rings (erythema marginatum)

Note: Symptoms of headache and substantial fatigue may be checked by the subject but play no role in the characterization of the location of a subject-reported attack.

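### The exemption of HAE attacks from adverse-event reporting makes no exception for fatal or life-threatening attacks, and it conflicts with the protocol's own interim SAE counts

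*Protocol*

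**What the plan says.** Protocol 12.1.1.1 states that "HAE attacks and their associated symptoms will not be defined as AEs, even if the subject requires hospitalization". It gives the reason and the alternative record: "All HAE attacks and associated symptoms are reported in the subject diary and are a reflection of the disease under study". Events that trigger an attack, such as infection or trauma, remain AEs. Worsening of a pre-existing condition is an AE only when the condition is not the one under study, so that route is closed to attacks.

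Protocol 12.1.1.2 begins: "A SAE is an AE/reaction that results in any of the following outcomes". Death and threat to life head the list of outcomes. The 24-hour duty in 12.1.2 and 12.1.5 attaches to SAEs.

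Protocol 5.1 says of the disease: "Oropharyngeal swelling can be life-threatening". It adds that deaths still occur in diagnosed patients with access to specialist care.

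Protocol 5.2.2, the interim summary of this study, lists HAE attacks among the treatment-emergent SAEs (12 subjects), among the Grade 3 or 4 TEAEs (3.5%) and as a TEAE leading to interruption of study drug (5 subjects). It reports that no TEAE led to death.

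The proportions of subjects with treatment-emergent SAEs and with Grade 3 or 4 AEs are safety endpoints (Protocol 7.1.1, SAP 3.2.1). SAP 9.3.1 adds a count of subjects with a fatal SAE.

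**The concern.** The study's primary objective is safety, and the drug is given to prevent attacks. A fatal or airway-threatening attack is the worst form that failure of prevention can take. An investigator who follows 12.1.1.1 to the letter is told that such an event is not an AE and is given no instruction to report it within 24 hours.

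The routine record of attacks is no substitute for an expedited report. Under Protocol 11.2.2, "Diaries will be collected at each visit and at follow-up". Scheduled visits are 24 weeks apart after Week 24, monthly return is optional, and site staff may not make diary entries.

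There is also a problem of definition. If some attacks were counted as SAEs under one practice and later attacks are excluded under the written rule, the SAE and Grade 3 or 4 proportions mix two definitions. A fall in either could then reflect the counting rule and not the drug.

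**Working it through.** **Reading the rule**

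1. An attack and its symptoms are not AEs (12.1.1.1). The only aggravating outcome named is hospitalization, and it does not lift the exemption. Death and threat to life are not mentioned.
2. An SAE must first be an AE or reaction (12.1.1.2), so a serious outcome alone does not bring an exempt attack back in. The important-medical-event clause leaves room for judgement, but it does not mention attacks.
3. The 24-hour report (12.1.2, 12.1.5) and the fatal-SAE count (SAP 9.3.1) both depend on SAE status.
4. No other section restores fatal or life-threatening attacks. The chain therefore ends with no expedited report and no count for them.

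**Reproducing the interim figures** (Protocol 5.2.2, N = 227)

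- HAE attack as SAE: 12/227 = 5.3%, as stated (exact 95% interval 2.8% to 9.1%).
- Any treatment-emergent SAE: stated as 13.2%. Only 30/227 rounds to this.
- Any Grade 3 or 4 TEAE: stated as 15.0%, which is 34/227. HAE attack at Grade 3 or 4: stated as 3.5%, which is 8/227.
- Interruption due to a TEAE: 27/227 = 11.9%, of which HAE attack 5/227 = 2.2%. Both are as stated.

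**Applying the exemption strictly to the same data**

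Let T be the subjects with any event of the given type, A those with an HAE attack of that type, and b those among A who also had another event of that type. The proportion after exclusion is (T − A + b)/227, with b between 0 and A. The documents do not give b.

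| Measure | As reported (also b = A) | b = 0 |
|---|---|---|
| SAE | 30/227 = 13.2% | (30 − 12)/227 = 18/227 = 7.9% |
| Grade 3 or 4 TEAE | 34/227 = 15.0% | (34 − 8)/227 = 26/227 = 11.5% |
| TEAE leading to interruption | 27/227 = 11.9% | (27 − 5)/227 = 22/227 = 9.7% |

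The choice of rule can move the SAE proportion by at most 12/227 = 5.3 percentage points.

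**Scale in the full study**

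Assuming the interim proportion held in the planned 475 or so subjects, 475 × 12/227 ≈ 25 subjects would have an attack whose status as an SAE depends on which practice is followed. Applying the exact interval gives about 13 to 43. These are attack-SAEs under any seriousness criterion, not fatal or life-threatening attacks.

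**The case against.** Handling events of the disease under study as effectiveness data is a deliberate choice with a stated reason, and routine attacks need not be AEs. That stands, and the point does not dispute it.

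A reader might infer more than the documents support:

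- *That severe attacks reach neither the SAE endpoint nor the DMC in practice.* The interim summary shows attacks recorded as SAEs. SAP 5.1 says of the DMC material: "The packet will include study disposition, demographic, and safety information by treatment group". It includes SAE and Grade 3 or 4 tables by system organ class and preferred term, and reasons for withdrawal. No attack data are listed there, but the DMC Charter is not supplied and may add them. The SAP covers protocol versions only up to 5.0.
- *That airway attacks cannot be seen in the analysis.* SAP Table 6 places airway swelling within the peripheral or mixed location. Even so, symptoms are summarised for adjusted attacks and listed for all reported attacks (SAP 6.7.8.11), and professional care is summarised (SAP 8.3.1.5).
- *That the diary is the only record.* SAP 6.7.8.1 refers to an eCRF page for attack details, and Protocol 8.3.1 requires the reason for withdrawal, if known, in the CRF. Neither carries a 24-hour clock for an attack.
- *That all 12 subjects would leave the SAE count.* Some may have had another SAE.
- *That 12/30 = 40% of subjects with an SAE measures the harm.* The seriousness criteria for those 12 are not given, so the number with a life-threatening attack is unknown, and no TEAE was fatal.
- *That the protocol forces subjects off other prophylaxis.* Table 2 gives recommended strategies, and 9.7 lets users of C1-INH, tranexamic acid or lanadelumab continue. Oral androgens are the exception (9.7.1).

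Finally, the interim data come from earlier protocol versions whose AE wording is not supplied. The exemption may be newer than the data, or it may not have been followed. Either way, the current protocol sets a rule and reports counts that do not match it.

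**Conclusion.** The concern holds as a gap in the written rule and as an inconsistency in the definition of a safety endpoint. A fatal or life-threatening attack handled strictly by 12.1.1.1 and 12.1.1.2 has no 24-hour report and falls outside the SAE and fatal-SAE summaries. The interim summary in 5.2.2 counts attacks in a way that this rule does not allow. Depending on the rule applied, the interim SAE proportion lies between 7.9% and 13.2%, and the Grade 3 or 4 proportion between 11.5% and 15.0%.

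These ranges rest on the reported counts and on complete ignorance of overlap with other events. They measure the ambiguity in counting, not the frequency of fatal or life-threatening attacks, which the documents do not give. They do not show that any such attack went unreported. The gap still deserves correction, because one event handled by the letter of the text would make the safety record wrong.

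**What to change.** Reconcile Protocol 12.1.1.1, 12.1.1.2 and 5.2.2:

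1. In 12.1.1.1, limit the exemption to attacks that are neither fatal nor life-threatening.
2. State that a fatal or life-threatening attack is an SAE, to be reported under 12.1.5 within the existing 24 hours.
3. In the SAP, set one counting rule for HAE attacks in the SAE and Grade 3 or 4 endpoints and apply it to all protocol versions. Show the SAE proportion with and without HAE attacks, so that interim and final figures can be compared. No new table line for attack-SAEs is needed, because SAP 9.3.1 already tabulates SAEs by preferred term.
4. In 5.2.2, note the basis on which the interim attacks were counted.

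Optionally, unless the DMC Charter already provides it, add to the DMC packet a simple listing of attacks with airway symptoms or professional care sought, drawn from data already collected.

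The cost is a short protocol change, a site memo, one additional presentation of the SAE proportion and, if adopted, one DMC listing. The downside is a few more expedited reports. Other attacks stay exempt.

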7.1. Endpoints

7.1.1. Safety Endpoints

The primary objective of the study is to obtain long-term safety of BCX7353. The safety endpoints will include the following:

- The proportion of subjects who discontinue BCX7353 due to a TEAE
- The proportion of subjects with treatment-emergent SAEs
- The proportion of subjects with TEAEs
- The proportion of subjects with treatment-emergent Grade 3 or 4 AEs
- The proportion of subjects with treatment-emergent, treatment-related AE consistent with a drug rash
- The proportion of subjects with treatment-emergent Grade 3 or 4 laboratory abnormalities

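### The list of hospitalizations exempt from SAE reporting includes one whose symptoms must be reported as an AE, so some planned or prolonged diagnostic stays may be recorded as non-serious

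*Protocol*

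**What the plan says.** Protocol Section 12.1.1.1 opens the exemption with a condition: "Hospitalization scenarios do not require reporting as an SAE where there is no occurrence of an AE". It then introduces examples: "These scenarios include a planned hospitalization or prolonged hospitalization to" do one of four things. The first example has two halves. One is routine control screening for an illness the subject already has. The other is a stay "to diagnose a suspected illness. In the case of the latter, the symptomatology should be reported as an AE", with the entry amended if a diagnosis is confirmed.

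Protocol Section 12.1.1.2 lists among the outcomes that make an AE serious: "Requires subject hospitalization (formal admission to a hospital for medical reasons) or prolongation of existing hospitalization". Later in the same section it says: "Some hospitalization scenarios, as outlined in Section 12.1.1.1 do not require reporting as SAEs".

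One of the six safety endpoints in Protocol Section 7.1.1 is "The proportion of subjects with treatment-emergent SAEs". SAP Sections 3.2.1 and 9.3 carry it forward. Protocol Sections 12.1.2 and 12.1.5 require a report to the sponsor within 24 hours for SAEs.

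**The concern.** The second half of the first example does not meet the condition that introduces the list. If the symptoms are an AE, an AE has occurred, and the stated ground for exemption is gone. The example still stands in the exempt list, and Section 12.1.1.2 points to that list without restating the condition. A site that reads the example on its own terms can enter the symptoms as a non-serious AE although the subject was admitted. A site that reads the opening condition strictly will report an SAE for the same case.

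Long-term safety is the primary objective, and the SAE count also feeds the DMC packet (SAP Section 5.1). A case recorded as non-serious leaves the SAE tables and does not trigger the 24-hour report. Misclassification by this route can only reduce the SAE count.

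**Working it through.** The plan gives no figure for this point, and Protocol Section 13.1 states that no sample size was calculated. The check is a comparison of texts, followed by a scale calculation.

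**Texts side by side**

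1. Section 12.1.1.1 defines a sign or symptom that develops or worsens during the study as an AE.
2. The exemption in the same section is conditional on there being no AE.
3. The diagnostic example requires its symptoms to be reported as an AE. If the opening condition governs, the example exempts nothing. It has effect only if it exempts an admission that accompanies an AE.
4. A neighbouring example keeps the condition explicitly: "Undergo medical observation without the occurrence of an AE due to standard of care in the region or hospital". The elective-procedure example is limited to a known condition that has not changed. The diagnostic example carries no such limit.
5. Section 12.1.1.2 makes an AE with admission or a prolonged stay serious and does not separate planned from unplanned admission. It then adopts the Section 12.1.1.1 scenarios.
6. The instruction to amend the entry concerns the reported term. Nothing in that example tells the site to reassess seriousness.
7. The SAP counts events already classified as SAEs. It has no rule that would recover admitted AEs recorded as non-serious.

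**Scale, using the interim data in Protocol Section 5.2.2**

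- Inputs: 227 treated subjects; 13.2% with a treatment-emergent SAE.
- Count: 0.132 × 227 = 29.96, so 30 subjects; check, 30/227 = 13.2%.
- Effect of one subject whose only SAE is recorded as non-serious: 1/227 = 0.44 percentage points. At the planned global enrolment of about 475, 1/475 = 0.21 points.
- Assumed range, because the documents give no count of diagnostic admissions: with 1 missed subject, (30 + 1)/227 = 13.7%; with 5, (30 + 5)/227 = 15.4%, against the reported 13.2%.

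The range of 1 to 5 is illustrative and not an estimate. Protocol wording may also have differed in the versions under which the interim data were collected.

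**The case against.** The strongest reply is that the opening condition governs the whole list. The examples illustrate admissions without an AE, and the reference in Section 12.1.1.2 imports the condition along with the list. On that reading the instruction to report the symptoms as an AE is a safeguard: once there is an AE, the ordinary seriousness test applies. Reporting something as an AE does not make it non-serious, since Section 12.1.1.1 ends by saying that AEs are designated one or the other. The instruction to amend the entry matches the general rule on updating terms in Section 12.1.2.

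This reading is available to an investigator, and it limits the point. A reader might infer that the exemption simply overrides Section 12.1.1.2, so that every hospital work-up of new symptoms leaves the SAE count. The documents do not support that. The list covers only planned admissions and prolonged stays, so an unplanned admission is not clearly exempt, and the opening condition still permits an SAE report. The word planned is not tied to a date before consent or first dose, however, so an admission scheduled for symptoms that arose on drug fits the example. Prolonged stays are listed separately.

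A reader might also take one of the three interim subjects with drug-related SAEs, treat that admission as diagnostic, and conclude that the exemption would have removed it. All three were reported as SAEs, and nothing says their admissions were planned or diagnostic. The interim SAEs also included 12 subjects with HAE attacks and 3 with medical observation, types that the current text excludes or exempts. The interim data therefore give no sign of under-reporting.

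Other capture remains. The events stay on the AE form and in the TEAE endpoint, and count in the Grade 3 or 4 and discontinuation endpoints where those apply. The important-medical-event criterion is open, at the investigator's discretion. ALT or AST elevations above 3 × ULN have their own confirmation and monitoring rule in Section 12.2.2. None of this restores the SAE classification or the 24-hour report.

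**Conclusion.** The conflict is real. A condition and one of its own examples contradict each other, and the SAE definition defers to the list that contains both. Planned admissions and prolonged stays to diagnose new on-drug symptoms may be recorded as non-serious AEs, without expedited reporting and not uniformly across sites. The direction is known, towards fewer SAEs. The size is 0.44 points per affected subject at 227 and 0.21 at 475, assuming the subject has no other SAE. The total is unknown because the number of such admissions is not given.

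This is an ambiguity in a reporting definition that touches a primary-objective endpoint. It merits correction, but it is not a defect that puts the study's safety conclusions in doubt: its scope is limited to planned and prolonged stays, and the events remain visible as AEs.

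**What to change.** Reconcile Sections 12.1.1.1 and 12.1.1.2 in one of two ways:

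- delete the words on diagnosing a suspected illness, and the sentence that follows them, from the exempt list; or
- keep the item but limit it to conditions known before first dose and unchanged.

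In either case add a sentence on these lines: an AE that leads to admission or a prolonged stay is assessed against the Section 12.1.1.2 seriousness criteria from admission, and its term is updated if a diagnosis is made. HAE attacks and their symptoms must be excepted, because Section 12.1.1.1 says they are not AEs even when the subject is hospitalized. Without the exception, work-up of an abdominal attack would become an SAE for something that is not an AE.

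Before the final analysis, query AEs recorded as non-serious that involved a hospital admission, where the data allow admission to be identified. The documents do not show whether the AE form records it, so the effort for this step is uncertain.

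The cost is a short wording amendment, a few more SAE forms, and possibly a slightly higher reported SAE proportion.
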